10.0 Beta Blockers Dosage and Titration

Subjects will be assessed for BB therapy uptitration at Day 14 (+/-1) follow up.

11.0 Adverse Events or Unanticipated Problems involving Risk to Participants

All incidence of AE, AE leading to withdrawal of IP, and SAE will be reported to the IRB per institutional policies and procedures. IP will be stopped in treatment emergent clinically relevant events such as hypotension, significant dizziness, loss of consciousness, atrial fibrillation, 3rd degree AV block, and QTc prolongation. If IP is stopped, no re-challenging will be done. In case of any events between the scheduled study visits, subjects will be instructed to call the 24/7 phone number of the study team, and if clinically relevant, subjects will be asked to come in to follow up clinic for an unscheduled visit.

11.1 Unblinding Procedure

In the case of an emergent medical event, where the unblinding of a subject is deemed medically necessary by the study PIs, the unblinded study personnel will consult the randomization key to unblind study treatment. Once a subject has been unblinded, the date, time and reason(s) for un-blinding will be recorded in the source documents and eCRF.

11.2 MedWatch Reporting

If in the study PIs assessment, an unexpected SAE is related to subject's participation in the study, the event will be reported to MedWatch.

11.3 Data Safety and Monitoring Board

A safety analysis and review by an independent 3-member data safety and monitoring board (DSMB) will be done halfway through recruitment (after 66 subjects have been enrolled). Based on the outcomes of the review, the DSMB may propose amendments to the study protocol. The study PIs will review these proposals prior to amending the protocol and submitting to the IRB.

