2.0 Rationale

Ivabradine (IVA) has been shown to decrease the risk of hospitalizations for worsening HF and was associated with a trend towards improved mortality in the SHIFT¹ trial. SHIFT¹ excluded patients within 4 weeks of hospital discharge, so the efficacy and safety of IVA in this setting is less clear. In today's health care environment more and more patients that present to the ED for mild AHF are being placed into observation unit and subsequently discharged, or discharged outright from the ED. This is not only a growing segment of patients, but also represents an important window of opportunity to intervene with a potentially effective therapy.

Moreover, at this point in a patient's experience (being discharged after getting treated for exacerbation of HF), it's not clear that beta blockers (BB) should yet be increased/started due to the recent state of exacerbation. Standard treatment of worsened heart failure presenting to the ER or urgent care includes diuresis and vasodilators (e.g. ACE-I), but according to usual standard of care, titration of beta blockade is often reserved for outpatient follow up after a period of demonstrated stability (in the ambulatory setting). This is in contradistinction to hospitalized patients, where patients have been observed by the treating team for days, presumably show stability and improvement, and starting low dose BB at the time of hospital discharge has been shown to be safe (IMPACT-HF² trial). As such these ED/Observation discharge patients are often not optimal candidates for intensification of BB at the time of release, and could be considered to be at maximally tolerated BB dose (for at least for 2-4 weeks). This may represent a vulnerable period for these patients; it's unknown in the setting of Observation discharge but evidence from hospitalized patients indicates that the highest daily risk of rehospitalization is in the days just after discharge. IVA may be effective post observation unit management (where lower risk HF patients are typically placed), to reduce heart rate (without decreasing contractility, such as a BB would) to help reduce the risk of hospitalization or emergency care, but safety and efficacy (in terms of heart rate lowering) in this setting has not been previously explored.

Additionally, the SHIFT¹ trial lacked African Americans and this unique patient population has not been previously studied with IVA. The investigating sites serve a predominantly African American patient

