14.0 Sample Size And Power

Based on the SHIFT¹ study, the mean heart rate reduction with IVA is 8 bpm with a standard deviation of 13 bpm. A sample size of 57 in each group will have 90% power to detect a difference in means of 8.0 assuming that the common standard deviation is 13.0 using a two group t-test with a 0.05 two-sided significance level. To account for a projected dropout rate of 15%, 66 subjects will be enrolled in each group (132 total for the study over a 2-year period). Furthermore, we expect that our centers will recruit a cohort that is 75% self-identified African Americans. This number (n=99) will provide 80% power to detect the same effect size when analyzed in African Americans only.

For the safety endpoint (unplanned presentation for medical care), assuming an event rate of 25% at 1 month (estimated based on local hospital readmission rates), our sample size will provide 80% power to detect a doubling of the relative risk. If the Control group event rate is higher there will be greater power; for example, with an event rate of 35% we would have 98% power for risk ratio of 2.0 and 83% power for risk ratio of 1.75.

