STATISTICAL ANALYSIS PLAN: OBSERVE-IVA

A Randomized, Double-Blind, Placebo-Controlled Trial
Assessing the Efficacy of Ivabradine Initiated at the
Time of Discharge from the Observation Unit

NCT: 03168529
8/1/2021

[name]
[contact]

Statistical Analysis Plan:

**A Randomized, Double-Blind, Placebo-Controlled Trial Assessing the Efficacy of Ivabradine Initiated at the Time of Discharge from the Observation Unit.
(OBSERVE-IVA)**

NCT: 03168529

The original plan detailed in the protocol is as follows:

13.0 Statistical Analysis The primary outcome (change in heart rate i.e. the value at Day 28 (+/-2) - the value at baseline) will be analyzed as two sample t-test. Secondary outcomes that are continuous variables will be analyzed as two sample t-test. The safety endpoint of unplanned visits will be compared as the number of unplanned medical visits over the study period tested using Poisson regression.

14.0 Sample Size And Power Based on the SHIFT1 study, the mean heart rate reduction with IVA is 8 bpm with a standard deviation of 13 bpm. A sample size of 57 in each group will have 90% power to detect a difference in means of 8.0 assuming that the common standard deviation is 13.0 using a two group t-test with a 0.05 two-sided significance level. To account for a projected dropout rate of 15%, 66 subjects will be enrolled in each group (132 total for the study over a 2-year period). Furthermore, we expect that our centers will recruit a cohort that is 75% self-identified African Americans. This number (n=99) will provide 80% power to detect the same effect size when analyzed in African Americans only.

Unfortunately, formal statistical analysis was not completed due to low sample size. Unfortunately, OBSERVE IVA fell far short of its enrollment goal with just 19 out of a targeted 132 subjects included in the final study cohort. Because of this, we have not developed any abstracts, manuscripts or other publications to date, though we may do so in the future. Of the 19 enrollments, 6 were at Detroit Receiving Hospital, 8 at Sinai-Grace Hospital, 2 at Harper University Hospital, and 3 at Henry Ford Hospital. A total of 13 subjects (68%) received ivabradine (IVA) and 6 received matching placebo.

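### The only planned DSMB review is triggered solely by the 66th enrolment, with no calendar or event-based alternative, so slow accrual leaves it never due.

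*Protocol*

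**What the plan says.** Protocol Section 11.3 assigns a safety analysis and review to an independent board of three members. On timing it says only that this "will be done halfway through recruitment (after 66 subjects have been enrolled". The board may then propose protocol amendments, which the study PIs consider before going to the IRB.

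Section 14.0 sets the enrolment plan: "132 total for the study over a 2-year period". The SAP reports the outcome: "just 19 out of a targeted 132 subjects included in the final study cohort". Of these, 13 received ivabradine and 6 placebo.

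Section 2.0 gives the reason safety deserves attention here. The reference trial left out patients in the first 4 weeks after hospital discharge, "so the efficacy and safety of IVA in this setting is less clear".

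Other oversight is described elsewhere. Section 11.0 sends adverse events, events leading to withdrawal of study drug, and serious events to the IRB. Section 11.1 allows emergency unblinding of individual subjects. Section 11.2 covers MedWatch reporting of unexpected serious events that the PIs judge related. Section 15.0 requires annual IRB continuing review.

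**The concern.** A trigger set only by a head count works if recruitment keeps pace. If recruitment is slow, the trial stays open longer and the review moves further away. If recruitment stops short of the count, the review never falls due. Section 11.3 has no fallback for either case, and none appears elsewhere in the protocol or SAP.

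The DSMB is the only body to which the documents give a safety analysis of accumulating data. What is at stake is whether anyone in that role looks across the subjects treated so far in a setting that the protocol itself describes as uncertain on safety. The events for which Section 11.0 stops study drug include loss of consciousness, atrial fibrillation, third-degree AV block and QTc prolongation. A board can usefully consider such events one by one, even when numbers are too small for a test.

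**Working it through.** **Inputs.** Trigger: 66 enrolled (Section 11.3). Target: 132 over 2 years (Section 14.0). Enrolled: 19, of whom 13 received ivabradine (SAP). The actual accrual period is not given, so 24, 36 and 48 months are assumed below, with even accrual.

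**1. The plan's own figure.** 132/2 = 66, which matches Section 11.3.

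**2. Planned timing.** 132/24 = 5.5 subjects per month, and 66/5.5 = 12 months. On plan, the review falls at about month 12.

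**3. When the trigger fails within the 2-year window.** It is missed if accrual is below 66/24 = 2.75 per month. That is 2.75/5.5 = 50% of plan, so the weakness could be seen at the design stage.

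**4. What was reached.** 19/66 = 28.8% of the trigger; 19/132 = 14.4% of the target.

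**5. Effect of a 12-month backstop at the observed enrolment.** Rate = 19/months; time to 66 = 66/rate; subjects at the first review = 12 × rate.

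| Assumed accrual period | Rate per month | Months to reach 66 | Subjects at month 12 | 12-month anniversaries reached |
|---|---|---|---|---|
| 24 months | 0.79 | 83 | 9.5 | 2 |
| 36 months | 0.53 | 125 | 6.3 | 3 |
| 48 months | 0.40 | 167 | 4.8 | 4 |

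The last anniversary in each row falls as enrolment closes. Without it the counts are 1, 2 and 3. The existing trigger gives none in any row.

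**6. Would there be anything to review?** Suppose an event of interest has probability p per ivabradine subject over the 28 days (p is an assumption). The chance of at least one among 13 is 1 − (1 − p)^13: 49% at p = 5%, 75% at p = 10% and 95% at p = 20%. These figures cover the whole trial, not the first meeting alone. Case-level review could well have had material.

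**7. Exposure at any one time.** Over 24 months, 19 × 28 days / 730 days = 0.73 subjects on study treatment (either arm) on average, and fewer over a longer period.

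**The case against.** The strongest reply is that the practical gap is small. Treatment lasts 28 days, and on average fewer than one subject was on study treatment at a time. A first annual review would see about 5 to 10 subjects over both arms, too few for a useful comparison. A count-based trigger also tracks cumulative exposure, so slow accrual means fewer people treated before a review. At that scale, protection comes mainly from handling individual events, and the protocol provides for this: criteria for stopping study drug, a 24-hour telephone line, unscheduled visits, emergency unblinding and IRB reporting. All of this stands, and it keeps the severity low. It does not supply a safety analysis of accumulating data by an independent board.

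Three stronger readings are tempting, and the documents do not support them:

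- A reader might infer that no DSMB review took place. The documents show that the trigger was not reached. They do not say whether the board met on another basis, or whether it had been constituted.
- A reader might infer that subjects had no independent safety oversight. Sections 11.0 and 15.0 provide IRB event reporting and a calendar-based annual IRB review.
- A reader might infer that an unblinded look at harms by arm was lost. Section 11.3 promises a safety analysis and review, and does not say that it is unblinded or split by arm.

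**Conclusion.** The gap is real and of minor severity. Followed exactly as written, Section 11.3 yields no DSMB review at 19 enrolled, and would yield none within 2 years at any accrual below half of plan. IRB reporting and annual IRB review reduce the consequence but are not given the DSMB's task.

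The failure of the trigger follows from the documents' own counts and needs no assumption. The estimates of how many reviews a backstop would add, and how many subjects each would see, rest on the assumed accrual periods of 24 to 48 months and on even accrual. The benefit is case-level review of events, since the numbers would not support a formal comparison.

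**What to change.** Change the timing in Section 11.3 so that the DSMB safety review takes place after 66 subjects are enrolled or 12 months after the first enrolment, whichever comes first, and every 12 months after that while enrolment remains open.

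On plan, the first review coincides with the existing one. Tying the repeats to open enrolment matters: if they ran until the last subject's Day 28 (about month 25 on plan), a month-24 meeting would be required just as recruitment ends. With the wording above, the on-plan cost is essentially nil. With slow accrual it is about one short meeting a year. The sample size, the efficacy analysis and all treatment rules are unchanged.

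For the completed trial, the sponsor should record whether the DSMB met and, if so, on what data.

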12.0 Biomarker Assessments

Once patients have been enrolled they will have their blood drawn using proper phlebotomy procedures. Standard gold top serum vacutainer and green top Lithium Heparin gel vacutainer, approximately 10mL (about 2 tsp) of blood, will be drawn at baseline as well as at the day 28 (+/- 2) (visit 3) follow-up. Plasma vacutainers will be placed in the refrigerator (2°-8°C) while serum sample is coagulating for 30-60 minutes. Immediately after the serum sample has coagulated for at least 30 minutes the vacutainers will be centrifuged in a swing bucket horizontal centrifuge for 10 minutes at 1100 to 1300 g. Samples will be qualitatively assessed for hemolysis after centrifugation. These characteristics will be recorded in the source documents. Plasma and serum will be aliquoted using transfer micro pipettes into as many 0.5 mL aliquots possible; aseptic techniques will be utilized throughout processing. These aliquoted samples will be frozen in a -80°C freezer onsite within three hours of blood draw. Samples will be batch shipped on dry ice in thermally-insulated containers to the University of Maryland. Good Laboratory Practices and national regulations regarding biohazardous materials will be followed. NT-proBNP and hs-TnT levels will be quantified.

13.0 Statistical Analysis

The primary outcome (change in heart rate i.e. the value at Day 28 (+/-2) - the value at baseline) will be analyzed as two sample t-test. Secondary outcomes that are continuous variables will be analyzed as two sample t-test. The safety endpoint of unplanned visits will be compared as the number of unplanned medical visits over the study period tested using Poisson regression.

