1.0 Summary

Prospective, randomized (1:1), placebo-controlled, double blind, study of ivabradine (Corlanor®) begun at the time of discharge from the hospital or observation unit after a stay of < 48 hours from the time of admission, for a total of 28 (+/-2) days in a cohort of predominantly (but not exclusively) African American patients with acute heart failure (HF). The primary endpoint will be change in heart rate from discharge to 28 (+/-2) days. Secondary endpoint will be heart rate change in African Americans from discharge to 28 (+/-2) days. Exploratory endpoints include change in NT-proBNP, change in hs-cTnT each comparing baseline to 28 (+/-2) days. Key safety endpoints will be the rate of unplanned medical care (presentation to ED or urgent care, unplanned hospitalization, unplanned medical office visit) and days alive and out of hospital over the 28 (+/-2) days of treatment.

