5.0 Endpoints

Efficacy:

- Primary - Change in heart rate (Day 28 (+/-2) - baseline), measured by 12-lead ECG and Zio® patch (Day 14 (+/-1) - baseline).
- Secondary - Change in heart rate in self-identified African Americans (Day 28 (+/-2) – baseline), measured by 12-lead ECG and Zio® patch³(Day 14 (+/-1) - baseline).
- Exploratory:
 - 1) Change in NT-proBNP (Day 28 (+/-2) – baseline)
 - 2) Change in hs-cTnT (Day 28 (+/-2) – baseline)

Safety: Presentation for unplanned medical care in any setting within 28 (+/-2) days.

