Baseline data for the overall study cohort and by randomization are provided in the accompanying **Table** with corresponding notation regarding the approach to statistical analysis. While no formal comparison has been performed, data showing heart rate at each of the 3 study visits for the 19 subjects enrolled and by study group are provided in the accompanying **Figure**.

Table: Baseline data for OBSERVE IVA study cohort

Figure: Heart rate trends by study visit (1= baseline, 2 = 15 days, 3 = 30 days)

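### The planned t-tests on heart-rate change are valid but use baseline heart rate only by subtraction; for the 19 enrolled, the SAP text gives no between-arm difference with a 95% CI

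*Protocol*

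**What the plan says.** Section 1.0 describes the trial as "Prospective, randomized (1:1), placebo-controlled, double blind". The primary endpoint in section 5.0 is "Change in heart rate (Day 28 (+/-2) - baseline), measured by 12-lead ECG", with a Zio patch measure at Day 14 as well. The schedule in section 8.0 places a 12-lead ECG at baseline, Day 14 and Day 28. Section 13.0 plans the primary comparison of change thus: "the value at baseline) will be analyzed as two sample t-test". It applies the same test to continuous secondary outcomes and names no covariate.

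Section 14.0 rests on "the mean heart rate reduction with IVA is 8 bpm with a standard deviation of 13 bpm" and asks for 57 per group for 90% power, raised to 66 for 15% dropout. For the secondary analysis it states: "This number (n=99) will provide 80% power to detect the same effect size when analyzed in African Americans only".

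The SAP repeats the analysis and the heart-rate sample-size text, then reports that "formal statistical analysis was not completed due to low sample size". It gives the arm sizes: "A total of 13 subjects (68%) received ivabradine (IVA) and 6 received matching placebo". On outcomes it says: "While no formal comparison has been performed, data showing heart rate at each of the 3 study visits" are in a figure, by study group. The contents of that figure and of the baseline table are not visible in the text available for this review.

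**The concern.** There are two separate points.

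**Design.** A change score fixes the slope of Day 28 on baseline heart rate at 1. If the true slope differs from 1, part of the baseline variation stays in the outcome as noise that a covariate would remove. The African American analysis has the least room: its stated 80% power is what remains after 15% dropout.

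**Reporting.** The SAP gives low enrolment as the reason for no formal analysis. A small sample makes a test uninformative, but it does not prevent stating the planned contrast. A wide interval is how that contrast carries its uncertainty. As the text stands, a reader has no difference in mean change, no interval and no count of patients with a Day 28 value. Anyone pooling this small trial with others would need all three.

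**Working it through.** **Inputs from the documents.** Difference 8 bpm, SD 13 bpm, two-sided alpha 0.05, 57 per arm, 15% dropout, 66 per arm enrolled, 99 African Americans (section 14.0); 13 v 6 enrolled (SAP).

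**Assumed, because the documents do not give them.** Correlation rho between baseline and Day 28 heart rate: 0.3, 0.5, 0.7. Baseline SD (SD0): either equal to the Day 28 SD (SD1), or 10 bpm. Section 4.0 requires a heart rate of at least 70 at entry, which truncates the baseline distribution, so a smaller baseline SD is plausible. The 13 bpm is read as the SD of change, the natural reading of section 14.0.

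**1. The plan's own figures** (noncentral t, difference 8, SD 13).
- 57 per arm: 90.3%. The stated 90% reproduces.
- 66 × 0.85 = 56 per arm: 89.8%.
- 99 × 0.85 / 2 = 42 per arm: 79.6%. The stated 80% reproduces after dropout; with all 99 evaluable it is 85.8%.

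**2. What adjustment can gain.**
- Variance of change = SD0² + SD1² − 2·rho·SD0·SD1 = 13² = 169.
- Residual variance after adjustment = SD1²(1 − rho²).
- The gap between them is SD0²(1 − b)², where b = rho·SD1/SD0 is the baseline slope. It is never negative and is zero when b = 1.

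SD1 is solved so that the SD of change stays at 13. Adjusted power uses the residual SD and one fewer degree of freedom.

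| SD0 | rho | SD1 | slope b | residual SD | variance reduction | power, 56/arm | power, 42/arm |
|---|---|---|---|---|---|---|---|
| = SD1 | 0.3 | 11.0 | 0.30 | 10.48 | 35% | 97.9% | 93.3% |
| = SD1 | 0.5 | 13.0 | 0.50 | 11.26 | 25% | 96.1% | 89.6% |
| = SD1 | 0.7 | 16.8 | 0.70 | 11.99 | 15% | 93.8% | 85.6% |
| 10 | 0.3 | 11.8 | 0.35 | 11.29 | 25% | 96.1% | 89.4% |
| 10 | 0.5 | 14.7 | 0.73 | 12.73 | 4% | 90.9% | 81.2% |
| 10 | 0.7 | 17.9 | 1.25 | 12.76 | 4% | 90.8% | 81.0% |
| t-test on change | – | – | fixed at 1 | 13.00 | – | 89.8% | 79.6% |

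**3. The planned contrast for those enrolled** (SD of change 13).
- 13 v 6: SE = 13 × √(1/13 + 1/6) = 6.42; t with 17 df = 2.110; half-width 13.5 bpm.
- 11 v 5 (the plan's 15% loss applied to each arm): SE 7.01; t with 14 df = 2.145; half-width 15.0 bpm.
- Power for 8 bpm at 13 v 6: 21.8%.

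**4. Would adjustment help at 13 v 6?** Simulation with 40,000 replicates, SD of change 13. The mean unadjusted half-width is 13.3 bpm, because the average sample SD falls slightly below 13.

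| SD0 | rho | mean adjusted half-width (bpm) | share of replicates where adjusted is narrower |
|---|---|---|---|
| = SD1 | 0.3 / 0.5 / 0.7 | 11.1 / 12.0 / 12.7 | 89% / 78% / 61% |
| 10 | 0.3 / 0.5 / 0.7 | 12.0 / 13.5 / 13.6 | 78% / 33% / 31% |

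The large-sample guarantee also needs equal allocation if slopes differ by arm. With assumed slopes of 0.5 (ivabradine) and 1.2 (placebo), and baseline and residual SD of 10, the variance of common-slope ANCOVA relative to the change score is 0.980 at 1:1 but 1.060 at 13:6.

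**The case against.** The strongest reply is that nothing is wrong. A t-test was planned, a t-test was powered, and the numbers agree. Preferring ANCOVA is a matter of efficiency, and the gain depends on inputs the documents do not supply. With baseline SD 10, two of the three scenarios gain only 4%, and the entry threshold makes a restricted baseline spread plausible. All of this stands, and it is why the point is minor.

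The documents do not support three stronger readings that a reader might infer.

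- **That the trial was underpowered because 13 bpm is a single-visit SD.** On that reading, with equal SDs at both visits, the t-test would need 79, 57 or 35 per arm for rho 0.3, 0.5 or 0.7. Section 14.0 attaches the SD to the heart-rate reduction, so this reading is the less natural one and the conclusion here does not rest on it.
- **That ANCOVA should now replace the t-test for the 19 enrolled.** The SAP already displays heart rate by study group, so changing the lead analysis would be a data-aware choice. At 13 v 6 it might not narrow the interval either.
- **That the SAP conceals a result.** It says openly that formal analysis was not done, why, and how many were in each arm. It also refers to a figure by arm, and to a table with notes on statistical approach. The gap identified here concerns the visible text only.

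It is also fair to say that an interval of about ±13.5 bpm against an 8 bpm target will probably be inconclusive. That is a reason to make no claim of significance, but it does not justify omitting the estimate.

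**Conclusion.** The point holds as a low-severity improvement. The planned tests are valid and correctly powered; the loss is of efficiency, with no bias. Under the planned 1:1 design, baseline adjustment is asymptotically at least as precise and gains nothing if the slope is 1. The range of 4% to 35% in variance rests on an SD of change of 13 bpm and on the assumed correlations and baseline SDs. None of that gain is available with 19 patients.

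For those patients, what remains is a modest reporting gap: the visible SAP text does not state the prespecified contrast with its uncertainty. The half-width of ±13.5 bpm assumes all 19 have a Day 28 value, which the text does not say; it is wider if some are missing.

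**What to change.** **Plan as designed, or any reuse of it.** In section 13.0, regress Day 28 (±2) 12-lead ECG heart rate on arm and baseline ECG heart rate, for the primary and the African American secondary analyses. Keep the t-test on change as a sensitivity analysis. The cost is wording and one degree of freedom.

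**The 19 enrolled.** Keep the prespecified unadjusted difference in mean change as the lead analysis. Report it with its 95% CI and the number per arm with a Day 28 value, as estimation only, with no claim of significance. A baseline-adjusted difference is optional; if given, label it post hoc and note that its interval may be no narrower. The cost is one t-interval on the heart rates recorded by visit and, if wanted, one regression.

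### The primary t-test on change uses only patients with a Day-28 value, ignores the Day-14 ECG and uses baseline only by subtraction; a baseline-adjusted repeated-measures model is more precise, but does not by itself cure informative loss

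*Protocol*

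**What the plan says.** Protocol Section 5.0 defines the endpoint as "Primary - Change in heart rate (Day 28 (+/-2) - baseline), measured by 12-lead ECG and Zio® patch (Day 14 (+/-1) - baseline"). Section 13.0 says the Day 28 minus baseline change "will be analyzed as two sample t-test", and the SAP repeats this. Section 14.0 sizes the trial for the same test: "A sample size of 57 in each group will have 90% power to detect a difference in means of 8.0". The SD there is taken as 13 bpm in both arms, and the test is two-sided at the 5% level. Loss is handled only through the sample size: "To account for a projected dropout rate of 15"%, the 57 per group becomes 66.

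Neither document names an analysis set, a missing-data rule, a covariate or a sensitivity analysis. The Section 8.0 schedule has a 12-lead ECG at baseline, Day 14 and Day 28. Section 7.0 includes an ECG at Visit 2 but leaves it out of its Visit 3 list.

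On stopping study drug, Section 11.0 says "IP will be stopped in treatment emergent clinically relevant events such as hypotension", among other events. Section 9.0 stops it at any time for a heart rate below 50 with symptoms. Neither section says that such a patient leaves follow-up.

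**The concern.** A patient without a Day-28 heart rate has no change score. With no imputation or modelling rule, the stated test is in effect an analysis of completers. Two things are lost. Baseline heart rate enters only by subtraction, which is less efficient than using it as a covariate unless the between-visit correlation is very high. The Day-14 ECG, available for anyone lost after Visit 2, is not used at all.

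Loss may also not be random. Several reasons for stopping study drug relate to what the drug does to heart rate. If some of those patients then miss Day 28, the completers in the ivabradine arm could have higher heart rates than the full arm, and the estimated reduction would be pulled toward zero. At stake are the width of the primary confidence interval and, to a smaller degree, where it is centred.

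**Working it through.** **Inputs from the documents.** Difference 8 bpm, SD 13, two-sided 0.05, 57 evaluable and 66 enrolled per group, 15% loss (Section 14.0); allocation 1:1 (Section 1.0).

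**Assumed, because the documents do not give them.** 13 is taken as the SD of change. The correlation ρ of baseline with each follow-up visit is 0.3, 0.5 or 0.7; the Day 14 to Day 28 correlation is 0.1 higher; the SD is the same at each visit. The loss mechanisms are hypothetical.

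**1. The plan's own figure.** The normal approximation gives 2 × (1.960 + 1.282)² × (13/8)² = 55.5, so 56. The noncentral t gives 56.5, so 57, with power 90.3%. The stated figure reproduces. 57 × 1.15 = 65.6, so 66 (dividing by 0.85 would give 68). Expected completers are 66 × 0.85 = 56.1 per arm, with power 89.8%.

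**2. Precision under random loss.** For the t-test, SE = 13 × √(2/56.1) = 2.45. If 13 is the SD of change, one heart rate has SD σ = 13/√(2(1−ρ)). After adjustment for baseline, the residual SD is σ√(1−ρ²) = 13√((1+ρ)/2), so the SE is multiplied by √((1+ρ)/2):

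| ρ | factor | SE, baseline-adjusted (formula) | SE simulated: t-test / baseline-adjusted completers / repeated measures |
|---|---|---|---|
| 0.3 | 0.806 | 1.98 | 2.45 / 1.97 / 1.96 |
| 0.5 | 0.866 | 2.13 | 2.44 / 2.09 / 2.05 |
| 0.7 | 0.922 | 2.26 | 2.52 / 2.32 / 2.25 |

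(66 per arm, 3,000 runs per row.) Power rises from about 90% to 94–98%. Baseline adjustment alone gives 93–98%, so the Day-14 value adds little precision.

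**3. Bias if loss follows the recorded Day-14 heart rate.** Suppose 15% of the ivabradine arm is lost after Visit 2, favouring low Day-14 values, and placebo loss is random. The most extreme case is a sharp cut-off, which raises the retained patients' mean Day-14 value by 0.233/0.85 = 0.274 SD (0.233 is the normal density at the 15th percentile). The change score moves with the Day-14 value by the difference of the two correlations, here 0.1. The bias is therefore at most 0.1 × 0.274 × σ. With σ = 10.99, 13.0 and 16.78, this is 0.30, 0.36 and 0.46 bpm. Simulation with a gradual rather than sharp dependence gave 0.2–0.3 bpm. The size is proportional to the assumed 0.1 gap.

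**4. Mean estimates by loss pattern** (true value −8; ranges over ρ = 0.3–0.7; 15% loss):

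| Loss in the ivabradine arm | t-test | Repeated-measures model |
|---|---|---|
| After Visit 2, follows low recorded Day-14 heart rate | −7.7 to −7.8 | −8.0 |
| Follows later heart rate that is never recorded | −6.5 to −7.0 | −6.3 to −6.9 |
| Before the Day-14 ECG | −7.7 to −7.8 | −7.0 to −7.4 |

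A harsher split (30% lost on ivabradine, none on placebo) shows the same pattern. The t-test and model biases are 0.4–0.8 and 0.0–0.1 bpm in the first case, 2.0–2.8 and 2.4–3.3 in the second, and 0.3–0.7 and 1.2–2.3 in the third.

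**5. Why the model can do worse.** Subtracting baseline cancels much of a patient's persistent level; adjusting for it cancels less. At ρ = 0.5 with loss before Day 14, the change score follows the unseen Day-14 value with slope 0.6 − 0.5 = 0.1, and the baseline-adjusted value with slope 0.6 − 0.5 × 0.5 = 0.35. No Day-14 value exists to correct the latter.

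**The case against.** A reader might infer that a repeated-measures model removes bias whenever bradycardia or symptoms drive loss. The documents do not support that. Section 9.0 allows study drug to be stopped at any time and Section 11.0 foresees events between visits, so the trigger need not appear on the Day-14 ECG, and symptoms are not in the model. Steps 4 and 5 show that the model can then be the more biased of the two. It also keeps only those lost patients who attended Visit 2.

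A reader might also infer that the strongest responders are lost from the primary analysis. Sections 9.0 and 11.0 stop study drug; they do not end follow-up. A patient off drug can still supply a Day-28 ECG to the t-test. Whether such values are collected and used is the first thing to settle.

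A third temptation is to cite the larger bias of a baseline-adjusted analysis of completers. Neither document plans that analysis, so it is not evidence against the planned t-test.

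One further objection stands. Section 9.0 ties Day-14 changes in study drug or beta blocker to heart rate at that visit. The relation between Day 14 and Day 28 may therefore be non-linear and differ by arm, while the model uses one linear covariance. The simulations did not examine this.

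Finally, the t-test bias in the favourable case is small, about a tenth of its SE, and conservative. That is true, and the argument for change rests mainly on precision and on the missing-data rule that the plan lacks.

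**Conclusion.** The point holds as a moderate weakness of the plan. The stated primary test is unadjusted, restricted to patients with a Day-28 value, and leaves the Day-14 ECG unused. Under random loss the cost is an SE of about 2.4–2.5 instead of about 1.95–2.3 bpm, nearly all of it recoverable by baseline adjustment. The bias is about 0.2–0.3 bpm toward zero if ivabradine loss after Visit 2 follows low recorded Day-14 heart rate.

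These sizes rest on assumed correlations of 0.3–0.7, a 0.1 higher correlation between the follow-up visits, and hypothetical loss mechanisms. The model is unbiased only if loss depends on recorded heart rates, so the sensitivity analysis is part of the recommendation.

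The point concerns the plan, not a result: the SAP reports 19 of 132 enrolled (13 ivabradine, 6 placebo) and no formal analysis. At those numbers the t-test has about 22% power for 8 bpm, and no choice of model would rescue it.

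**What to change.** - Section 13.0 and the SAP: make the primary analysis a repeated-measures model of ECG heart rate at Day 14 and Day 28, with arm, visit, arm-by-visit, baseline heart rate and baseline-by-visit terms and unstructured covariance. Include all randomised patients with at least one post-baseline ECG. The Day-28 contrast is primary.
- State that Day-28 ECGs are collected and used after study drug is stopped, and say which treatment effect this makes the analysis estimate.
- Reconcile the Section 7.0 Visit 3 list, which omits the ECG, with the Section 8.0 schedule, which includes it.
- Keep the two-sample t-test as a supportive analysis.
- Add a missing-not-at-random sensitivity analysis: shift the missing Day-28 values by a range of deltas, by arm, and report where the conclusion changes. Tabulate reasons for and timing of loss by arm.

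The cost is protocol and SAP text and some extra programming; no new visit or measurement is needed. The downside is reliance on missing-at-random given recorded heart rates. Where that fails the model can be more biased than the t-test, so all three analyses should be reported together.
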